## 4.7 Efficacy Evaluation

### 4.7.1 Analysis and Data Conventions

Confidence intervals will be calculated at the two-sided 95% level of confidence except for the primary efficacy and safety endpoints which will be one-sided 99% and 95% respectively.

This study is designed to test for non-inferiority of GC5107 which will be compared with historically-based standards. The null hypothesis is that the incidence of serious acute bacterial infections in subjects treated with GC5107 is greater than or equal to 1.0 per subject per year. The alternative hypothesis is that the incidence of serious acute bacterial infections is less than 1.0 per subject per year. Symbolically, this is expressed as follows:

H0: average incidence of serious acute bacterial infections on GC5107  $\geq$  1.0 per subject per year

H1: average incidence of serious acute bacterial infections on GC5107  $<$  1.0 per subject per year

A one-sided test based on a generalized linear models procedure for Poisson regression with  $\alpha=0.01$  will be used to test this hypothesis. Equivalently, the upper one-sided 99% confidence limit would be less than 1.0.

Adverse Event related efficacy endpoint are defined based on treatment emergency adverse event (TEAE) only, including acute serious bacterial infections, infection other than acute serious bacterial infections, incidence of infections, duration of infections, time to resolution of infection.

#### 4.7.1.1 Multi-center Studies

For the purpose of the summaries and analyses, the term ‘Site’ will be used to define each investigator site.

For the primary efficacy variable, the statistical model to be used for the estimation of treatment effects will not adjust for differences between centers. Adjustment for center will not be performed in the analysis of the secondary efficacy variables.

#### 4.7.1.2 Adjustments for Covariates

Not applicable.

#### 4.7.1.3 Handling of Dropouts or Missing Data

#### 4.7.1.6 Examination of Subgroups

The uniformity of the treatment effect for the primary efficacy and primary safety variables will be examined for the following subgroups:

1. Age ( $\geq 2$  to  $< 12$  years,  $\geq 12$  to  $< 17$  years,  $\geq 17$  years)
2. Sex (Male, Female)
3. Race (White, Black or African American, Asian, American Indian or Alaska Native, Native Hawaiian or Other Pacific Islander, Other)
4. Geographic region (United States, Non-United States)

Summaries of the primary efficacy and primary safety variable by subgroup will be produced based on the ITT population. Same summaries by subgroup will be repeated, based on the ITT2 population. No formal statistical test will be performed within subgroups.

#### **4.7.2 Primary Efficacy Variable – Incidence of Acute Serious Bacterial Infections**

The primary variable for the assessment of efficacy is the incidence of acute serious bacterial infections (pneumonia, bacteremia and septicemia, osteomyelitis/septic arthritis, bacterial meningitis, visceral abscess) per subject during the 12-month study observation period, calculated for the ITT population. The primary variable will be analyzed by infusion schedule and overall.

A formal statistical analysis (a non-inferiority test) will be applied for the primary efficacy endpoint. A 99% one-sided upper confidence limit for the incidence of serious acute bacterial infections will be derived, and conformance with the FDA standard will be considered acceptable if this limit is less than 1.0 per subject per year.

To estimate the event rate and develop the appropriate one-sided 99% upper confidence limit, a generalized linear models procedure for Poisson regression will be used. This will allow for the possibility of over-dispersion resulting from extra-Poisson variation. This procedure involves estimating a scale parameter of over-dispersion [4]. The mean event rate is estimated by regressing the response on a vector of 1's. Event rates for individuals will be calculated by dividing the number of events for that individual by the total amount of follow-up time. The distribution of these event rates across individuals will be presented using a histogram.

A secondary analysis will also be conducted, assuming a Poisson distribution for the occurrence of primary endpoints, with no over-dispersion. The first step is calculating the annualized infection rate observed for each subject. The annualized infection rate for each individual will be calculated by dividing the number of events for that individual by his or her amount of follow-up time.

These infection rates will be transformed using a square root transformation (since the data are expected to be approximately Poisson), and the mean and variance calculated, weighting by the number of months data available for each subject. The upper 99% one-sided confidence limit for the population mean (on the transformed scale) will then be calculated using standard normal distribution theory, and the resulting limit will be squared (to back-transform it to the original scale) for comparison with the target value of 1 per subject per year.

The influence of outliers will be investigated by repeating the primary analysis with any outlying values excluded.

Total amount of follow-up time for each subject is defined as (date of last visit – first infusion date + 1)/365.25 for subjects who complete the study; and defined as (date of withdrawal – first infusion date + 1)/365.25 for subjects who withdraw from the study.

A sensitivity analysis to assess the robustness of the study conclusions to the choice of analysis population will be performed on the PP population and ITT2 population for the primary efficacy variable.

The homogeneity of the treatment effect for a number of important subgroups (i.e. age, sex, race) will be investigated as described in 4.7.1.6.

A by-subject listing of the primary efficacy data will be provided.

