#### **4.11 Changes in the Conduct of the Study or Planned Analysis**

Any deviation from the procedures described within this analysis plan will be described in the clinical study report. Per FDA’s request, ITT2 population is added into the analysis plan. ITT2 population will be used to perform a sensitivity analysis of the primary efficacy and primary safety endpoints. FDA also requested to add subgroup of geographic region (United States, non- United States) as well as age, sex and race which were planned initially, to evaluate the uniformity of the treatment effect for the primary efficacy and primary safety variables. Protocol section 9.1.7. specified the following planned analysis for AEs that occur during an infusion: “the time AEs change materially in intensity and/or resolve” will be reported and analyzed. In the SAP section 8.4.3, the planned analysis had been modified to “the time of AEs duration,” as the exact time of AE changing intensity is not collected in the eCRF. Only AE duration is available to analyze the time AEs resolved.

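### The supportive square-root analysis of serious bacterial infections does not give a 99% upper limit for the mean rate, and with a few events its limit lies below the observed rate

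*SAP*

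**What the plan says.** SAP section 4.7.1 sets the hypothesis on the average incidence of serious acute bacterial infections, with a margin of 1.0 per subject per year. The decision rests on this: "A one-sided test based on a generalized linear models procedure for Poisson regression", at one-sided alpha 0.01. The SAP adds: "Equivalently, the upper one-sided 99% confidence limit would be less than 1.0". Section 4.7.2 repeats the rule for the over-dispersed model: conformance with the FDA standard "will be considered acceptable if this limit is less than 1.0 per subject per year".

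Section 4.7.2 then describes a second analysis: "A secondary analysis will also be conducted, assuming a Poisson distribution for the occurrence of primary endpoints, with no over-dispersion". Its steps are:

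1. Divide each subject's event count by that subject's follow-up time.
2. Take roots: "These infection rates will be transformed using a square root transformation (since the data are expected to be approximately Poisson").
3. Calculate the mean and variance of the roots, weighted by months of data.
4. Form the 99% one-sided upper limit for the mean root by normal theory.
5. Back-transform: "the resulting limit will be squared (to back-transform it to the original scale) for comparison with the target value of 1 per subject".

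The section gives no bias correction at step 5.

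**The concern.** The hypothesis and the 1.0 target concern the mean rate. The square of a limit for the mean root is a limit for a different and smaller quantity. The report would therefore show two figures side by side, both described as 99% upper limits and both set against 1.0, of which the second does not have that meaning.

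Two things are at stake. At low counts the supportive limit overstates precision, and it can lie below the rate observed in the same trial. At higher true rates it can fall below 1.0 when a valid limit would not, and so appear to support a primary result that is borderline or negative.

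**Working it through.** **Inputs.** The one-sided 99% level (z = 2.3263), the 1.0 margin, the Poisson assumption and the transformation steps are from SAP 4.7.1 and 4.7.2. The sample size of 42 to 50 is from the protocol synopsis. Follow-up of 12 months, taken as one year each, is from SAP section 3. The text available for this review gives no expected infection rate and no dropout rate, so both are varied below as assumptions. Variance is read as the sample variance of the roots, because the SAP says it is calculated.

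**What the squared limit bounds.** Since Var(√X) = E[X] − (E[√X])²,

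(E[√X])² = E[X] − Var(√X).

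- Poisson mean 1.0: E[√X] = 0.773 and Var(√X) = 0.402, so the square is 1.0 − 0.402 = 0.598.
- Poisson mean 0.10: E[√X] = 0.097 and Var(√X) = 0.0906, so the square is 0.100 − 0.0906 = 0.009.

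The gap does not depend on n. Only the half-width shrinks with n, so more subjects make coverage worse. At a true rate of 1.0 and expected moments (SD = √0.402 = 0.634), the limit is

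- n = 42: (0.773 + 2.326 × 0.634/√42)² = 1.002;
- n = 50: (0.773 + 2.326 × 0.634/√50)² = 0.964.

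The typical limit therefore sits at or below 1.0 when the true rate is 1.0.

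**A worked low count: 2 events in different subjects, n = 42.** Mean root = 2/42 = 0.0476. Sample variance = (2 − 2²/42)/41 = 0.0465, so SD = 0.2155 and SE = 0.2155/√42 = 0.0333. Limit = (0.0476 + 2.3263 × 0.0333)² = 0.0156. The exact limit is χ²(0.99; 2(X+1))/(2T) = 16.81/84 = 0.200.

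The same calculation for other counts (n = 42, one year each, events in separate subjects):

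| Events | Observed rate | Square-root limit | Exact Poisson limit |
|---|---|---|---|
| 0 | 0 | 0 | 0.110 |
| 1 | 0.024 | 0.006 | 0.158 |
| 2 | 0.048 | 0.016 | 0.200 |
| 5 | 0.119 | 0.056 | 0.312 |
| 10 | 0.238 | 0.154 | 0.480 |

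The square-root limit was below the observed rate at every count checked from 1 to 21 events with n = 42, and from 1 to 30 with n = 50.

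**Does it have its stated 99% level?** Poisson trials were simulated, 100,000 to 200,000 per setting. The runs agree to within about one percentage point.

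| True rate | Coverage, n = 42 / 50 | Square-root limit passes, exact fails, n = 42 / 50 |
|---|---|---|
| 0.10 | 6% / 3% | at most 0.01% |
| 0.5 | 23% / 16% | 8% / 5% |
| 0.8 | 40% / 32% | 76% / 81% |
| 1.0 | 51% / 42% | 48% / 57% |

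Coverage was 68% or less at every rate checked from 0.02 to 1.4. At a true rate of exactly 1.0 the square-root limit is below 1.0 in about 49% (n = 42) and 58% (n = 50) of trials. The exact limit is below 1.0 in 0.9% and 0.7%. An over-dispersed Poisson model limit (log link and Pearson scale assumed) is below 1.0 in about 0.8% to 0.9%.

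**Sensitivity at a true rate of 1.0.**

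- t in place of z: coverage 55% / 45%.
- 0 to 20% of subjects leaving uniformly between months 1 and 12 (an assumption): the limit is below 1.0 in 49–52% of trials (n = 42) and 57–61% (n = 50).
- Gamma-Poisson over-dispersion with shape 1: the limit is below 1.0 in 69% / 77%.

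None of these restores 99% coverage.

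**The case against.** The strongest reply is that little depends on this analysis. Success rests on the over-dispersed Poisson model, and the plan gives the supportive analysis no power to override it. If the true rate is low, both limits are far below 1.0. The square-root limit passes where the exact limit fails in at most 0.01% of trials at rates up to 0.3, and in 0.8% (n = 42) or 0.3% (n = 50) at 0.4. Disagreement becomes common only from about 0.5 upward, and the available text gives no expected rate to say how likely that is. This stands, and it limits the point to a supportive analysis. It does not make the reported limit valid.

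The second reply concerns the variance. The paragraph assumes Poisson data without over-dispersion, for which the root has approximate variance 1/4 at one year of follow-up. With that value and n = 42, the limits for 0, 1 and 2 events are 0.032, 0.041 and 0.052. The last two lie slightly above the observed 0.024 and 0.048. The lowest-count examples therefore depend on using the sample variance, which is the natural sense of a variance that is calculated. The alternative does not rescue the method: by 3 events its limit is again below the observed rate (0.063 against 0.071), and coverage at a true rate of 1.0 falls to about 32% (n = 42) and 25% (n = 50).

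Third, the exact limit is not the only valid choice. A Poisson model with the scale fixed at 1 would also match the analysis announced. That is fair, although with a log link it yields no finite limit when there are no events.

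**Conclusion.** The concern holds. Followed exactly, the supportive analysis yields a limit for the squared mean root rather than for the mean rate, and the plan compares it with 1.0 as if it were a 99% limit for the rate. At the null boundary its coverage is about 51% (n = 42) or 42% (n = 50), and it falls below 1.0 in about half of trials or slightly more. With a few events it lies below the observed rate; with none it equals zero.

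These figures assume one year of follow-up per subject, Poisson counts and the sample variance of the roots. The low-count table also assumes events in separate subjects. The algebra needs none of these assumptions. The primary analysis and the formal decision are unaffected. The point should be fixed because the figure will be reported beside the primary limit and cannot be defended as a 99% limit.

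**What to change.** Replace the square-root procedure in SAP 4.7.2 with the exact one-sided 99% Poisson limit,

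χ²(0.99; 2(X+1)) / (2T),

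where X is the total number of acute serious bacterial infections and T is the sum of the subjects' follow-up years. The section already supplies the definition needed for T, in the sentence that begins "Total amount of follow-up time for each subject is defined as". This is the Poisson analysis without over-dispersion that the paragraph announces. It handles unequal follow-up without weights and gives a positive limit with zero events. State that it is supportive and that success is judged on the over-dispersed model.

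The text of protocol section 9.1.4 was not available for this review. If it describes the square-root method, record the change in SAP 4.11. That section opens with "Any deviation from the procedures described within this analysis plan will be described in the clinical study report", and it already notes one departure from an analysis planned in the protocol.

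The cost is SAP wording, one line of code and possibly the entry in 4.11. No new data are needed. The supportive limit becomes larger, and so less favourable, but valid.

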## SYNOPSIS

STUDY TITLE	An Open-Label, Single-Arm, Historically Controlled, Prospective, Multicenter Phase III Study to Evaluate the Safety, Efficacy and Pharmacokinetics of Immune Globulin Intravenous (Human) GC5107 in Subjects with Primary Humoral Immunodeficiency
SPONSOR	Green Cross Corporation [name]
INVESTIGATIONAL PRODUCT	Immune globulin intravenous (human) solution, 10% liquid, GC5107
CLINICAL TRIAL DESIGN	Phase III, open label, single-arm, historically controlled prospective, multicenter study
INDICATION AND CLINICAL USE	Treatment of subjects with primary humoral immunodeficiency (PHID)
OBJECTIVES	To assess the safety, efficacy, and pharmacokinetics (PK) of GC5107 in subjects with PHID
INFUSION RATE	
First infusion:
 
Initial rate: 1.0 mg/kg/min (0.01 mL/kg/min) for 30 minutes
 
Incremental rate:
 

• 2.0 mg/kg/min (0.02 mL/kg/min) at 30 minutes

• 4.0 mg/kg/min (0.04 mL/kg/min) at 60 minutes

• 8.0 mg/kg/min (0.08 mL/kg/min) at 90 minutes

 
If the first infusion is well tolerated, infusions 2-13(17):
 
Initial rate: 2.0 mg/kg/min (0.02 mL/kg/min) for 15 minutes
 
Incremental rate:
 

• 4.0 mg/kg/min (0.04 mL/kg/min) at 15 minutes

• 8.0 mg/kg/min (0.08 mL/kg/min) at 30 minutes

 
Maximum rate: 8.0 mg/kg/min (0.08 mL/kg/min)

STUDY POPULATION
	
 
• Male or female aged 2 to 70 years with PHID requiring immune globulin intravenous (IGIV) treatment
 
• Total Number of Subjects: Up to 50 subjects will be enrolled to obtain at least 42 subjects to be included into the study: 
 
○ Adults: at least 26 subjects
 
○ Adolescents: at least 8 subjects aged <math>\geq 12</math> to <math>< 17</math> years
 
○ Children: at least 8 subjects aged <math>\geq 2</math> to <math>< 12</math> years
 
 
 
• PK population: at least 20 adult and adolescent subjects
 
• Subjects already stabilized (trough level of 500 mg/dL) on regular IGIV treatment
 

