### 2.1 Primary Efficacy Endpoint/Variable

- The incidence of acute serious bacterial infections meeting United States Food and Drug Administration (FDA) guidance criteria (bacterial pneumonia, bacteremia/sepsis, bacterial meningitis, visceral abscess, osteomyelitis/septic arthritis) [3]. The upper one-sided 99% confidence limit for the frequency of acute serious bacterial infections with GC5107 must be less than 1.0 per subject per year.

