## 3 INVESTIGATIONAL PLAN

This will be a prospective, open-label, single-arm, multicenter, historically controlled, Phase III study measuring the safety, efficacy, PK, and tolerability of GC5107 in subjects with PHID.

- The study design is an open-label, uncontrolled study of at least 26 adult subjects, at least 8 adolescent subjects aged  $\geq 12$  to  $< 17$  years and at least 8 child subjects aged  $\geq 2$  to  $< 12$  years with well-defined PHID.
- To guard against dropout and to assure more than adequate power, up to 50 subjects will be enrolled.
- All subjects will be followed for 12 months during which infusions will be given every 21 or 28 days.
- To demonstrate efficacy, the serious bacterial infection rate will be required to have an upper one-sided 99% confidence limit less than 1.0 per subject per year.
- Pharmacokinetics will be determined after the 5th study infusion.

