#### 4.4 Analysis Populations

The primary safety and efficacy analysis will be based on the intention-to-treat (ITT) population. The ITT population will consist of all subjects who are enrolled into the study and received any amount of investigational product.

The per-protocol (PP) population will also be analyzed for efficacy. The PP population will consist of all subjects in the ITT population who complete the whole 12-month study period and who do not have any major protocol violations, which are likely to have an impact on the validity of the data for analysis.

The intention-to-treat (ITT2) second population will consist of all ITT subjects who are enrolled into study following Protocol Version 2.0 amendment 1 (March 16, 2017) onwards. Subjects who are enrolled into study following Protocol Version 1.0 amendment 3 will be excluded. Protocol Version 2, Amendment 1 REB approval dates of each site is listed in Appendices. This population will be used to perform a sensitivity analysis for the assessment of the primary efficacy and safety endpoint.

All PK analyses will be based on the PK population. The PK population will be defined as a subset of adult and adolescent subjects in the ITT population who participate in the PK study and have at least one PK sample collected. At least 20 adult and adolescent subjects will be in the PK population. Blood samples required for PK analysis will be taken before and after the 5th study infusion for those subjects who consent to the PK portion of the study.

Upon database release, protocol deviation and analysis population outputs will be produced and will be sent to the Sponsor for review. An analysis population classification meeting (data review meeting) will be arranged to discuss the outputs and to decide which subjects and/or subject data will be excluded from certain analyses. Decisions made regarding the exclusion of subjects and/or subject data from analyses will be documented and approved by the Sponsor.

A summary of the number and percentage of subjects completing each visit of the study will be given overall for each analysis population (Analysis population: All Subjects Enrolled).

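### The outlier-excluded repeat of the primary analysis removes, in practice, subjects with serious bacterial infections, so it tests the result in almost only the favourable direction

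*SAP*

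**What the plan says.** The success criterion in SAP section 2.1 is that the upper one-sided 99% confidence limit for the rate of acute serious bacterial infections "must be less than 1.0 per subject per year". Section 4.7.1 ties this to a one-sided test at 0.01: "Equivalently, the upper one-sided 99% confidence limit would be less than 1.0". Section 4.4 fixes the analysis set: "The primary safety and efficacy analysis will be based on the intention-to-treat (ITT) population".

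Section 4.7.2 specifies an intercept-only Poisson regression with an estimated scale parameter: "This will allow for the possibility of over-dispersion resulting from extra-Poisson variation". The individual values are defined there as well: "Event rates for individuals will be calculated by dividing the number of events for that individual by the total amount of follow-up time". For a subject who withdraws, follow-up stops at the withdrawal date.

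The sentence at issue is in the same section: "The influence of outliers will be investigated by repeating the primary analysis with any outlying values excluded". The available text does not define an outlying value, give a threshold, say whether the unit removed is a subject or an event, name who decides, or say how the result is to be read. A separate sentence assigns the assessment of robustness to the PP and ITT2 populations.

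**The concern.** Excluding outliers is a sensible influence check when extreme values may be measurement errors and can lie on either side. Neither condition holds here. A subject's rate is bounded below at zero, and in a trial expected to succeed most subjects will be at zero. The values that stand out are then subjects who had a confirmed infection, that is, the treatment failures the endpoint exists to count. A subject who has one infection and withdraws early is especially exposed: one event in a quarter of a year is a rate of 1/0.25 = 4 per year.

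Removing such subjects lowers the rate and nearly always lowers the upper limit. The run therefore offers a positive primary result almost no chance of being contradicted. If the primary result failed, the run could show a limit below 1.0 that appears to blame a few unusual subjects. Because no rule is stated, which infections are dropped could be settled after the data are seen, in an open-label single-arm trial.

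**Working it through.** **Inputs from the documents.** Margin 1.0 per subject per year; one-sided alpha 0.01, so z = 2.326; Poisson model with an over-dispersion scale. Sample size from the protocol synopsis: "Up to 50 subjects will be enrolled to obtain at least 42 subjects to be included into the study" (26 + 8 + 8 = 42). Follow-up from SAP section 3: "All subjects will be followed for 12 months during which infusions will be given every 21 or 28 days".

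**Assumptions.** The text available for review includes neither the body of SAP section 4.10 nor the protocol's power table, so there is no planning rate to reproduce. True rates, heterogeneity and the outlier rule are assumed. Two common rules are compared: outside the 1.5 IQR fences, and more than 3 SD from the mean. Each subject has one year of follow-up. A log link is assumed, and a data set with no events counts as a pass.

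**Formula.** With m = events/subject-years, E = events and phi = Pearson chi-square/(n − 1):

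upper limit = m × exp(2.326 × √(phi/E)).

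**Step 1: which subjects are flagged.** Take 42 subjects, k of whom have one event each.
- IQR rule: both quartiles are zero for k up to 10, so the upper fence is zero and every affected subject is flagged.
- 3 SD rule, k = 4: mean 0.095, SD 0.297, cut-off 0.095 + 3 × 0.297 = 0.987. This is below 1, so all four are flagged.
- 3 SD rule, k = 5: mean 0.119, SD 0.328, cut-off 1.102. None is flagged.

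At k = 5 the full-data limit is 0.119 × exp(2.326 × √(0.902/5)) = 0.320. The IQR rule leaves 37 subjects and no events. The log-link estimate and its scale then do not exist; an exact limit would be −ln(0.01)/37 = 4.605/37 = 0.124.

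**Step 2: a failed result that becomes a pass.** Let six of 42 subjects have 6, 5, 4, 3, 2 and 1 events.
- Full data: m = 21/42 = 0.5 and phi = (80.5/0.5)/41 = 3.93. Limit = 0.5 × exp(2.326 × √(3.93/21)) = 1.37, a fail.
- 3 SD rule: the cut-off is 0.5 + 3 × 1.401 = 4.70, so the subjects with 6 and 5 events go (11 of 21 events). For the remaining 40, m = 10/40 = 0.25 and phi = (27.5/0.25)/39 = 2.82. Limit = 0.25 × exp(2.326 × √(2.82/10)) = 0.86, a pass.
- IQR rule: all 21 events go.

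**Step 3: simulation, 46 subjects, one year each.**

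| True rate | Events removed, IQR | Events removed, 3 SD | Pass, full data | Pass, IQR | Pass, 3 SD |
|---|---|---|---|---|---|
| 0.05 | 100% | about 80% | 100% | 100% | 100% |
| 0.1 | 99.7% | about 40% | 100% | 100% | 100% |
| 0.2 | about 83% | about 17% | 100% | 100% | 100% |
| 1.0, Poisson | about 10% | about 3% | about 1% | about 15% | about 2% |
| 1.0, gamma shape 0.5 | about 45% | about 18% | about 2% | about 63% | 11–12% |

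**Step 4: direction.** No pass became a fail under either rule, in these runs or in 50,000 further data sets with 42 subjects (ten scenarios of 5,000). Zero-event subjects were flagged only at a true rate of 1.0 without over-dispersion, under the IQR rule, in 0.7% of the 42-subject runs.

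**Step 5: the alternative on the same data.** In the Step 2 example, omitting one subject at a time gives these limits:
- without the 6-event subject: 0.366 × exp(2.326 × √(3.38/15)) = 1.10;
- without a zero-event subject: 0.512 × exp(2.326 × √(3.92/21)) = 1.40;
- without the 1-event subject: 0.488 × exp(2.326 × √(4.11/20)) = 1.40.

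The range is 1.10 to 1.40, against 1.37 on the full data. It shows influence in both directions, and no single subject accounts for the failure.

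**The case against.** The strongest defence is that nothing depends on this run. Success is judged on all ITT subjects with over-dispersion modelled, and the outlier run has no pass criterion. That stands. A reader might infer from the simulated pass rates that the trial's false-positive rate is inflated; the documents do not support this, because the confirmatory test uses every ITT event and nothing in the available text lets the outlier run overturn it.

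A reader might also infer that the plan deletes all the infections. The SAP states no rule, so that is too strong. Deletion is nearly complete under the IQR rule at low rates, but a 3 SD rule flags nobody once five of 42 subjects have one event each. Nor can an outlier only ever be a high value, as Step 4 shows.

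It is also fair that the SAP calls this an investigation of influence and places robustness elsewhere. Asking how far the estimate depends on a few subjects is legitimate. The planned histogram and by-subject listing keep every event visible. The failure to fit when no events remain depends on the assumed log link, and a trial with no infections would meet it in the primary analysis too.

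Finally, a reader might conclude that the plan has no analysis in the unfavourable direction, for example for early withdrawals. That cannot be said: the text of SAP sections 4.7.1.3 to 4.7.1.5 was not available.

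What remains is that the influence question is to be answered by excluding values that, on this endpoint, are in practice confirmed infections.

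**Conclusion.** The point holds as a defect in a supplementary analysis. Carried out as written, the run is close to one-sided: it cannot challenge a positive primary result and could make a failed one look acceptable. The primary ITT decision and its type I error are untouched.

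The direction is the same under both rules examined; the size is not. At a true rate of 1.0, the run's pass rate rises from about 1% to somewhere between 2% and 15%, or from about 2% to between 11% and 63% with strong heterogeneity (gamma shape 0.5). At true rates of 0.2 or below without over-dispersion, full and trimmed analyses both pass, so the check is uninformative there rather than misleading. These figures rest on assumed rates, heterogeneity, outlier rules, 46 subjects and one year of follow-up each. The change should be made, but the trial's validity does not depend on it.

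**What to change.** Delete the outlier-exclusion sentence from SAP section 4.7.2. State that all confirmed acute serious bacterial infections stay in every analysis of the subjects concerned, and that values are changed only to correct verified data errors.

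In its place, specify a descriptive leave-one-subject-out table on the ITT population. It should omit each subject in turn, refit the primary model, and report the range of the rate and of the upper one-sided 99% limit, identifying the subjects at the extremes. Label it as an influence display with no pass criterion.

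The cost is a few lines of SAP wording and one small programmed table. No new data are needed.
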